5.8. General Concomitant Medication and Supportive Care Guidelines

Concomitant care is not affected by this study. Subjects may receive full concomitant and supportive care.

5.9. Duration of Therapy

Therapy will consist of 60-66 Gy in subjects receiving conventional radiation therapy and 40-60 Gy in subjects receiving SBRT. All therapeutic doses delivered on this protocol are consistent with standard of care radiation therapy dosing.

Subjects will have research 4DCT scans and research pulmonary functions performed 3, 6, and 12 months post completion of radiation therapy. These visits will coincide with the standard of care clinic visits which occur every 3 months during year one.

5.10. Duration of Follow Up

Subjects will have life-long follow-up for this study to prospectively quantify radiation-related sequelae. The follow-up schedule is consistent with standard of care follow-up schedules for this patient population. The first study-defined follow-up appointment will be 3 months (10 week window: – 2 weeks to +8weeks) after completing radiation therapy. With approval of PI, subjects can miss this follow-up appointment and continue on the study.

Long term, follow-up will follow standard of care based on subjects disease status at each follow-up. Pertinent late radiation toxicities will be dictated by the treating physician and subsequently graded.

5.11. Adjuvant Therapy

Subjects who have left study, or who have completed their chemo-radiation treatment, may continue therapy at the discretion of their treating medical and radiation oncologists. This treatment is beyond the scope of the protocol, as these patients have completed participation in the protocol. Adjuvant therapy information will be collected for statistical purposes.

5.12. Assessments

- 5.12.1. Lung tissue elasticity evaluation using 4DCT.** Subjects will undergo research-ordered 4DCT scans at simulation, 3 months, 6 months and 12 months post-radiation.
- 5.12.2. Patient self-assessment** will be documented using a modified Borg scale, which has a history of use in pulmonary labs, with a scale of 1 (resting comfortably in a chair with no effort) to 10 (the most exertion and difficult breathing ever experienced).
- 5.12.3. Pulmonary Function Tests** will include FEV1, FVC, DLCO measurements
- 5.12.4. RTOG defined acute toxicity evaluation.** Evaluate both lung and esophageal toxicity. (Appendix B). Radiation Oncologist evaluation weekly during chemoradiation, at radiation therapy *fini*, and at 3-month follow-up.
- 5.12.5. RTOG late toxicity evaluation.** Evaluate lung, esophageal, skin, subcutaneous tissue, spinal cord, heart, and bone (Appendix C). Evaluation by Radiation Oncologist at 6 month follow-up and beyond.
- 5.12.6. Constitutional assessment:** quantify nausea, vomiting, diarrhea and other symptoms and any medications used for these symptoms. Done weekly during chemoradiation and at follow-up appointments.

6. DOSING DELAYS/DOSE MODIFICATIONS

Not applicable. If radiation dose needs to be modified or delayed, this is per standard of care and beyond the scope of this study. A note will be made in the study chart regarding any changes to radiation dose and any breaks in radiation therapy.

7. ADVERSE EVENTS:

The risks of harm for those subjects randomized to the research arm (arm 2) is equivalent to the control arm: optimized treatment plans in the research arm will be designed to meet the same dose specifications to organs-at-risk. In other words, when comparing the control and research arm:

- the same radiation doses will be delivered to the tumors
- the same radiation dose limits will be achieved for all normal tissues

There are minimal additional risks associated with the research procedures of 4DCT and PFT's.

The most significant risk from 4DCT is the increased radiation exposure which will be less than 1% of the dose received from the prescribed radiation therapy. Subjects may experience

discomfort from laying on their back during additional 4DCT scans. Each 4DCT scan will last 90 seconds. It is anticipated that patients will spend approximately 10-15 minutes on their back to position and collect the scans.

PFT's have the following associated risks: the test requires subjects to breathe in and out quickly, which may cause them to feel dizzy or faint. The test may increase the risk of asthma attack in those with asthma. In very rare cases, PFTs may cause a collapsed lung.

Patients will receive standard of care therapeutic radiation therapy dosing as part of this study. Toxicities associated with therapeutic radiation include: Reversible or permanent alopecia, bone marrow toxicity, skin reactions, and esophagitis are expected side effects of radiation therapy. Radiation-induced myocarditis or transverse myelitis rarely occur at doses lower than 50 Gy. Radiographic evidence of radiation change and subsequent fibrosis of the lung will occur within lung volume receiving first 6-12 months after initiation of treatment.

Acute (within 90 days post RT completion) and late radiation toxicities (> then 90 days post RT completion) will be recorded with special attention to the toxicities listed in appendix B and C. Any treatment interruption will be based on treating physician judgement and be documented as part of the study toxicity assessments.

7.1. Adverse Events Characteristics

This trial will be focused on the radiation toxicities experienced by patients who receive either SOC radiation treatment planning or the “optimized” treatment planning thus the toxicities recorded in this protocol will focus only on toxicities that can be at least possibly attributed to the radiation treatment.

RTOG (Radiation Therapy Oncology Group) has developed both acute and late radiation toxicities that occur in lung cancer patients. These toxicities and grading criteria are outlined in appendix B (acute toxicities) and Appendix C (late radiation toxicities).

In addition, 15% subjects who undergo chest radiation experience rib fractures. We will track rib fractures using the CTCAE 4.03 term “fracture” to ensure that “optimized” or experimental arm patients frequency and severity of fractures don’t exceed control arm subjects or historical frequency.

Changes in Pulmonary function tests

We will utilize the criteria used in RTOG0813 to quantify changes in pulmonary function testing.

RTOG0813 Criteria

Patients enrolled to this study are allowed to have some degree of impaired pulmonary function as measured by pulmonary function tests (PFTs), including Forced Expiratory Volume in 1 second (FEV1), Forced Vital Capacity (FVC), and Diffusing Capacity for Carbon Monoxide (DLCO). The Common Toxicity Criteria (CTCAE), v. 4 includes specified criteria for grading adverse events related to these PFT parameters under the system organ class of Investigations. The grading criteria for these PFT changes use the “percent predicted” values from 0-100% which are recorded on the patient’s PFT report. A percent predicted of 90% conveys that the patient is able to perform the PFT test to a

result that is 90% of what would be expected for the normal general population of the same height, age, and sex. The CTCAE version 4 specified grading criteria for PFTs assumes that all patients have normal baseline pulmonary function. This assumption is not appropriate for this protocol enrolling patients with abnormal baseline function.

As a remedy to monitor treatment effects on PFTs, we will define a protocol specific toxicity classification for PFTs that adjusts for baseline abnormalities. Changes that occur after therapy will be referenced to the baseline for a given patient, which will be abnormal for most patients. We have defined a proportional decline from the baseline. Grade 1 toxicity will be a decline from baseline to a level 0.90 times the baseline, grade 2 will be a decline to a level 0.75 of baseline, grade 3 will be a decline to a level 0.5 of baseline, grade 4 will be a decline to a level 0.25 of baseline, and grade 5 will be death. This scheme is depicted in the table below and graphically represented in the figure below. See appendix D

As an example, a patient who enters the study with a percent predicted DLCO of 55% who experiences a post treatment decline to a percent predicted DLCO of 40% would have a grade 3 event in the original CTCAE version 4 criteria; however, under this modified PFT toxicity classification for patients with abnormal baseline, his decline would constitute a decrease to 0.72 of the baseline value which is between 0.75 and 0.5 or a grade 2 event.

‘Expectedness’: AEs can be ‘Unexpected’ or ‘Expected’ for expedited reporting purposes only.

Attribution of the AE:

- Definite – The AE is *clearly related* to the study treatment.
- Probable – The AE is *likely related* to the study treatment.
- Possible – The AE *may be related* to the study treatment.
- Unlikely – The AE is *doubtfully related* to the study treatment.
- Unrelated – The AE is *clearly NOT related* to the study treatment.

Adverse Event Reporting

Adverse events (AEs) and serious adverse events (SAEs) will be recorded in study database. All SAEs will be reported to the lung DOWG, UWCCC, and UW HS-IRB per policy. Reporting criteria are summarized in Table 1.

An AE is an undesirable medical occurrence (sign, symptom, or diagnosis) or worsening of a pre-existing medical condition (diabetes, congestive heart failure, rheumatoid arthritis) that occurs after initiation of the investigational product whether or not it is considered to be investigational product related. A worsening of an existing medical condition is one that was present at baseline (e.g., cancer, diabetes, migraine headaches, gout) and became more severe, more frequent, or increased in duration during investigational product treatment. =

Expected events - Expected events are those that have been previously identified as resulting from treatment of lung cancer with radiation. These are defined above for

acute and late toxicities (section 8, appendix B and C). For purposes of this study, reporting requirements are determined by the assessment of the following adverse event characteristics: the type or nature of the event; the severity (grade); the relationship to the study therapy (unrelated, not likely, possibly, likely, or definitely related), and whether the event is expected or unexpected.

Recommended assessment steps include:

- Identification of adverse event.
- Determine whether the adverse event is expected or unexpected.
- Grading the severity of the adverse event using the appropriate set of criteria; CTCAE v.4.03 (General, unexpected).
- Determination as to whether the adverse event is related to the study therapy using the following categories: Unrelated, Possible, Probable, and Definite

For the purpose of this study acute radiation adverse event information will be collected through 90 day (3 month) post radiation visit. After the 90 day (3 month visit) visit only events specific late radiation treatment effects will be collected (appendix C) and any adverse events that result from the 4DCT and PFT's.

An SAE is defined by regulatory agencies as one that suggests a significant hazard or side effect, regardless of the investigator or sponsor's opinion on the relationship to investigational product. This includes, but may not be limited to, any event that (at any dose):

- Is fatal
- Is life threatening (places the subject at immediate risk of death)
- Requires inpatient hospitalization or prolongation of existing hospitalization
- Is a persistent or significant disability/incapacity
- Is a congenital anomaly/birth defect
- Any event that does not exactly meet this definition yet, in the investigator's opinion represents a significant hazard can be assigned the "other significant hazard" regulatory reporting serious criteria
- Additionally, important medical events that may not be immediately life threatening or result in death or hospitalization but that may jeopardize the subject or require intervention to prevent one of the outcomes listed above, or result in urgent investigation, may be considered serious. Examples include allergic bronchospasm, convulsions, and blood dyscrasias.

Note: All deaths on treatment require both routine and expedited reporting regardless of causality. Attribution to treatment or other cause must be provided. "On treatment" is defined begins with the radiation simulation planning session and ends 30 days post completion of radiation therapy.

All adverse events deemed to be related by the investigator to the radiation therapy as listed in section 8, appendix B and C will be collected and recorded throughout the study period beginning with the signing of the informed consent through the day patient is removed from the study or the date of death or 5 years after completion of the radiation therapy.

All serious adverse events that occur after the subject has signed the informed consent form must be reported to University of Wisconsin Carbone Cancer Center Data Safety and Monitoring Board and other regulatory agencies.

Grade 4 and 5 serious adverse events occurring greater than 30 days post RT AND thought to be possibly related to the RT or study procedures (4DCT's and/or PFT's) will be collected and submitted within 24 hrs with a full report within 10 working days of discovery or notification of the event via the same mechanism.

Table 1. Expedited reporting requirements for adverse events that occur within 30 days of the last dose of protocol RT and thought to be at least possibly related to protocol RT

FDA Reporting Requirements for Serious Adverse Events (21 CFR Part 312)

NOTE: Investigators MUST immediately report to the PI, UWCCC and UW IRB per policy ANY Serious Adverse Events, whether or not they are considered related to the investigational agent(s)/intervention (21 CFR 312.64). FDA Med Watch (3500A) will be submitted for grade 4 and 5 events at the discretion of the sponsor-investigator.

An adverse event is considered serious if it results in ANY of the following outcomes:

- Death.
- A life-threatening adverse event.
- An adverse event that results in inpatient hospitalization or prolongation of existing hospitalization for \geq 24 hours.
- A persistent or significant incapacity or substantial disruption of the ability to conduct normal life functions.
- A congenital anomaly/birth defect.

Important Medical Events (IME) that may not result in death, be life threatening, or require hospitalization may be considered serious when, based upon medical judgment, they may jeopardize the patient or subject and may require medical or surgical intervention to prevent one of the outcomes listed in this definition (FDA, 21 CFR 312.32; ICH E2A and ICH E6).

ALL SERIOUS adverse events that meet the above criteria* MUST be immediately reported to the UWCCC within the timeframes detailed in the table below:

Hospitalization	Grade 1 and Grade 2 Timeframes	Grade 3 Time Frames	Grade 4 & 5 Timeframes
Resulting in hospitalization \geq 24 hrs	Not required	10 Calendar Days	
Not resulting in Hospitalization \geq 24 hrs	Not required	10 Calendar Days	24 Hour; 5 Calendar Days

- See section 8.0, appendix B ,C and D for listing of toxicities
- Grade 3 toxicities resulting in hospitalization with attribution of probably or definitely related to chemotherapy will be exempt from expedited reporting

Expedited AE reporting timelines are defined as:

- **24-Hour; 5 Calendar Days** – The AE must initially be reported within 24 hours of learning of

the AE, followed by a complete expedited report within 5 calendar days of the initial 24-hour report.
 
 • 10 Calendar Days – A complete expedited report on the AE must be submitted within 10 calendar days of learning of the AE 
¹ Serious adverse events that occur more than 30 days after the RT dose and have an attribution of possible, probable, or definite related to radiation or other study procedures (4DCT and PFTs) require reporting as follows:
 
Expedited 24-hour notification followed by complete report within 10 working days for:
 
 • All Grade 4, and 5 AEs

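### Section 7.1 both restricts recorded toxicities to those attributed to radiation and calls for recording regardless of relatedness; if the restriction is applied, non-serious toxicity could be compared between arms through an attribution step with no described masking

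*Combined protocol and SAP*

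**What the plan says.** Four statements narrow what is collected.

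- Section 7.1, opening paragraph: "the toxicities recorded in this protocol will focus only on toxicities that can be at least possibly attributed to the radiation treatment".
- Section 7.1, on the collection period, where the investigator is named as judge and the toxicity scales themselves are covered: "All adverse events deemed to be related by the investigator to the radiation therapy as listed in section 8, appendix B and C" are what is collected and recorded. Section 8 now holds the correlative studies, so in practice the lists meant are the two appendices.
- Section 7.1, on late events: after the 90-day "visit only events specific late radiation treatment effects will be collected", together with events caused by the 4DCT scans and PFTs.
- Section 5.10: "Pertinent late radiation toxicities will be dictated by the treating physician and subsequently graded". The physician selects first and grading follows.

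Other statements carry no such filter.

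- Section 7.1, Adverse Event Reporting: "Adverse events (AEs) and serious adverse events (SAEs) will be recorded in study database". An adverse event is defined there as one that occurs after the intervention starts, "whether or not it is considered to be investigational product related".
- The attribution scale in Section 7.1 runs down to Unlikely and to Unrelated, the latter meaning "clearly NOT related".
- Sections 5.12.4 to 5.12.6 schedule RTOG acute grading, RTOG late grading and constitutional symptoms. Sections 10.3.4, 10.3.7 and 10.3.8 list these as collected data. None mentions attribution.

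Section 7.1 also says that rib fractures, put at 15% of subjects given chest radiation, will be tracked to ensure that Arm 2 does not exceed Arm 1 or the historical frequency.

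**The concern.** Both arms receive the same prescribed tumour dose under the same normal-tissue limits; only the planning differs (Sections 5.5.4 and 7). Whether an event is due to radiation is therefore not the between-arm question. Making it a condition of entry puts a subjective decision ahead of the comparison.

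That decision is hard in this population. Section 2.2 expects most patients to have other lung disease such as COPD, Section 3.2.3 excludes only severe COPD, and Section 5.6 leaves chemotherapy to the treating physician. Cough, dyspnea or dysphagia will often have more than one plausible cause. The radiation oncologist does the toxicity evaluation (Sections 5.12.4 and 5.12.5), and no section describes masking of patients, physicians or assessors. The amendment of 3/15/22 in Section 4.1 assigns the next 8 subjects directly to the optimized plan.

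An assessor who knows the arm and believes one plan spares lung may attribute events differently in the two arms. A difference in recorded toxicity could then reflect attribution rather than harm, and an event never entered may not be recoverable. Even without bias, staff cannot tell from the text which rule governs entry.

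**Working it through.** The plan gives no figure on this point, so there is none to reproduce. The check is a reading of the text followed by an illustration.

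**Which data could be filtered**

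| Data | What the text says | Exposed? |
|---|---|---|
| Serious adverse events | All those after consent are reported, with no relatedness condition (7.1) | No |
| PFT toxicity | Graded from the ratio to the subject's baseline (7.1, Appendix D) | No |
| 4DCT primary endpoint | Computed from images (10.1, 11.1) | No |
| Appendix B and C items, non-serious | Scheduled without attribution (5.12, 10.3), but recorded if deemed related (7.1) | Yes, if the 7.1 restriction governs |
| Other non-serious events | Recorded (7.1, reporting paragraph), but only if attributed (7.1, opening) | Yes, if the restriction governs |
| Rib fractures | Tracked with no stated attribution condition (7.1) | Only if the restriction is read to cover them |

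Rib fractures are open to both readings. The tracking sentence sets no condition, but bone fracture is also an Appendix C item, and the relatedness rule applies to Appendix C. Nothing states which passage prevails.

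**Illustration of size**

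Inputs:
- True rate p = 15% in both arms. The figure is from Section 7.1; its equality across arms is assumed.
- Shares of events attributed to radiation, a1 in Arm 1 and a2 in Arm 2. Both are assumed; the documents give none.

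Formula: recorded rate = p × a. The spurious difference is p × (a2 − a1), and the recorded ratio is a2/a1.

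| a1 | a2 | Arm 1 recorded | Arm 2 recorded | Difference (points) | Ratio |
|---|---|---|---|---|---|
| 90% | 90% | 0.15 × 0.90 = 13.5% | 13.5% | 0 | 1.00 |
| 90% | 80% | 13.5% | 0.15 × 0.80 = 12.0% | −1.5 | 0.89 |
| 90% | 70% | 13.5% | 0.15 × 0.70 = 10.5% | −3.0 | 0.78 |
| 90% | 50% | 13.5% | 0.15 × 0.50 = 7.5% | −6.0 | 0.56 |
| 70% | 90% | 10.5% | 13.5% | +3.0 | 1.29 |
| 50% | 90% | 7.5% | 13.5% | +6.0 | 1.80 |

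Conversely, the true Arm 2 rate that would look equal to Arm 1 is p × a1/a2. With a1 = 90% this is 0.135/0.80 = 16.9%, 0.135/0.70 = 19.3%, or 0.135/0.50 = 27.0%.

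Equal attribution lowers both recorded rates but leaves their ratio at 1. The ratio is distorted only when attribution differs by arm.

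**The case against.** The strongest reply is that the trial already grades the relevant items. RTOG lung and esophageal scores are taken weekly during chemoradiation, at the end of radiation and at 3 months; late scores at seven sites, including bone, follow from 6 months. The Appendix B lung grades rest on symptoms and findings, not cause. If these assessments are entered as scheduled, little is lost. This stands in part, because it shows the filter may not operate on those items. It does not settle the matter: Section 5.12 schedules the evaluation, whereas the restrictive sentences in Section 7.1 concern what is recorded and name the same appendices.

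A second reply is that a protocol may define adverse events broadly and collect them narrowly, so the definition alone is no contradiction. That is fair. The conflict rests mainly on the separate sentence that adverse events are recorded in the study database, and on attribution categories that would have little use for non-serious events under a strict filter.

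Third, a threshold of possible relatedness is low for thoracic symptoms after chest radiation, so few events may be excluded. Also, Section 11.1 lists toxicity among its endpoints only as determined by PFTs. Both points stand and limit the likely size and reach of the problem.

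A reader might infer that no toxicity of any kind enters the data without attribution, or that the safety comparison is biased in favour of Arm 2. The documents support neither. Several kinds of safety data are unfiltered, as shown above. Silence on masking does not prove that assessors knew the arm, and nothing in the documents shows that attribution differed by arm or in which direction.

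**Conclusion.** The point holds as a conflict in the text with a conditional risk of bias. The restrictive statements in Sections 5.10 and 7.1 cannot all be followed together with the unrestricted ones in Sections 5.12, 7.1 and 10.3, and no text says which prevails. This part rests on wording alone.

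The bias needs two conditions: that the restriction is applied at data entry, and that attribution differs by arm. The documents neither establish nor exclude the second. If both hold, the exposed data are non-serious, clinician-judged toxicities, with rib fractures included only on one reading. In the illustration the spurious difference runs from 0 to 6.0 points in either direction on a true rate of 15%; those sizes depend entirely on the assumed shares and are not estimates for this trial. The change is worth making because it is cheap and removes the possible bias, but nothing here touches the primary analysis.

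**What to change.** In Section 7.1, replace both restrictive sentences with a rule that every Appendix B and C item is recorded and graded at its scheduled visits, and every rib fracture whenever it occurs, regardless of attribution. Keep attribution as a separate field used for expedited reporting. State that any comparison between arms uses the all-cause grade. Align Section 5.10 and the late-event sentence in Section 7.1 with this rule, so that grading does not depend on a prior selection of events. Use one set of attribution categories throughout.

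The visits and scales already exist. The cost is a wording amendment, slightly more data entry, and some background events unrelated to radiation counted in both arms. Section 4.1 describes continuing accrual and Section 7.1 provides for collection up to 5 years after radiation, so the change would still affect data yet to be collected.
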